### **9.3.3 Assessment of outcome measures**

Major bleeding, defined as meeting one or more of the following ISTH criteria [[R05-0344](#), [P11-05406](#)]:

- Overt bleeding associated with a reduction in hemoglobin of at least 20 grams per liter or leading to a transfusion of at least 2 units of blood or packed cells
- Symptomatic bleeding in a critical area or organ: intraocular, intracranial, intraspinal, or intramuscular with compartmental syndrome, retroperitoneal bleeding, intra-articular bleeding or pericardial bleeding

Life-threatening bleeding, as defined as meeting one or more of the following criteria:

- Symptomatic intracranial bleed
- Reduction in hemoglobin of at least 50 grams per liter

- Transfusion of at least 4 units of packed cells, associated with hypotension requiring the use of intravenous inotropic agents
- Necessitated surgical intervention
- Fatal bleeding

Clinically relevant, non-major bleeding, defined as meeting one or more of the following ISTH criteria [[P15-12889](#)]

- Any sign or symptom of hemorrhage (e.g., more bleeding than would be expected for a clinical circumstance, including bleeding found by imaging alone) that does not fit the criteria for the ISTH definition of major bleeding but does meet at least one of the following criteria:
  - requiring medical intervention by a healthcare professional
  - leading to hospitalization or increased level of care
  - prompting a face to face (i.e., not just a telephone or electronic communication) evaluation

Recurrent DVT and/or PE: All recurrent VTE require objective verification by definitive diagnostic evaluation:

- any suspected DVT must be confirmed by venous compression ultrasonography conventional venography, CT or MRI to be entered as recurrent DVT in the CRF
- any suspected PE must be confirmed by one of the following: V-Q lung scan, pulmonary angiography, or spiral (helical) CT to be entered as recurrent DVT in the CRF

Deaths: Deaths will be classified as being:

- bleeding related (including bleeding events that contributed to deaths),
- VTE related (including VTE events that contributed to death based on investigator clinical judgment) and
- other.

ACS: will include ST elevation myocardial infarction (STEMI), non-STEMI (NSTEMI) and unstable angina (UA) [[P13-10618](#)].

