The primary comparative analyses will be based on the actual anticoagulation treatment the patients receive (i.e. “as treated” analysis). Patients who complete the planned anticoagulation treatment prior to one year or discontinue initial anticoagulation treatment permanently will be censored at date of last drug intake + 6 days for both dabigatran etexilate and VKA or at first intake of another relevant anticoagulation treatment, whichever occurs first. A patient is considered to have permanently stopped initial anticoagulation treatment if other relevant anticoagulation treatment is initiated or otherwise dependent on the duration of treatment interruption. Details of the censoring rules will be described in the SEAP.

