7.6 MAIN ANALYSIS

Analyses for the main outcome events are mainly defined for patients in the restricted patient set and, in some occasions for patients in the eligible patient set who took at least once the treatment. In general, recurrent events will be disregarded for the analyses of the outcomes.

Main outcome events – Incidence rates

For the treatment groups incidence rates with 95% CIs, cumulative risks, and KM curves will be calculated on the eligible patient set. Only patients from the eligible patient set that took the prescribed treatment at least once are considered. Patients who complete the planned anticoagulation treatment prior to one year or discontinue initial anticoagulation treatment permanently will be censored at date of last drug intake + 6 days for both DE and VKA or at first intake of another relevant anticoagulation treatment, whichever occurs first. A patient is considered to have permanently stopped initial anticoagulation treatment if other relevant anticoagulation treatment is initiated or if treatment has been interrupted for more than 30 days.

The main analysis of overall incidence rates with 95% confidence intervals, cumulative risks and KM curves will be repeated for the subgroups defined in Section 6.4. A graphical (forest-plot-like) display will additionally be prepared to summarize the subgroup results per outcome on the eligible patient set. Additional subgroup analyses might be conducted as needed.

For all important main and secondary outcomes for patients initiating VKA at baseline, and patients initiating DE at baseline, incidence rates, cumulative risks with 95%-confidence intervals will be calculated by treatment, and for a graphical comparison Kaplan Meier curves

will be plotted. These statistics will be calculated on the restricted patient set, and patients who never took the prescribed treatment will not be included. For the restricted patient set, as a sensitivity analysis, the calculation of incidence rates and cumulative risks will be performed without censoring at permanent discontinuation (intention to treat (ITT) approach). KM curves will be plotted.

Secondary and further outcome events

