Immobilization	True or False (CRF categories, medical history and concomitant diseases will be manually reviewed (past and concomitant))	N/A
Thrombophilia	True or False (CRF categories, medical history and concomitant diseases will be manually reviewed (past and concomitant))	N/A
Pregnancy and peri-partum period	True or False (CRF categories, medical history and concomitant diseases will be manually reviewed (3 month time window))	N/A

Concomitant use of aspirin	True or False (concomitant medication and other VTE therapies will be manually reviewed (concomitant))	N/A
Concomitant use of clopidogrel	True or False (concomitant medication and other VTE therapies will be manually reviewed (concomitant))	N/A
Estrogen therapy	True or False (concomitant medication and other VTE therapies will be manually reviewed (3 month time window))	N/A
Concomitant cancer	True or False (CRF categories, medical history and concomitant diseases will be manually reviewed (concomitant))	N/A
Hypertension	True or False (CRF categories, medical history and concomitant diseases will be manually reviewed (concomitant))	N/A
History of previous VTE	True or False (CRF categories, medical history and concomitant diseases will be manually reviewed (regardless of timing))	N/A
History of major bleeding or prior gastrointestinal bleed	True or False (medical history and concomitant diseases will be manually reviewed (regardless of timing))	N/A
Chronic renal disease	True or False (CRF categories, medical history and concomitant diseases will be manually reviewed (concomitant))	N/A

Patients who complete the planned anticoagulation treatment prior to one year or discontinue initial anticoagulation treatment permanently will be censored at date of last drug intake + 6 days for both dabigatran etexilate and VKA or at first intake of another relevant anticoagulation treatment, whichever occurs first. A patient is considered to have permanently stopped initial anticoagulation treatment if other relevant anticoagulation treatment is initiated or if treatment has been interrupted for more than 30 days.

Multiple imputation methods (e.g. the fully conditional specification method) will be used to impute both continuous and categorical variables appropriately with arbitrary missing patterns.

- b.) In addition, Cox regression analysis (based on the main analysis model) will be performed without censoring at permanent discontinuation (intention to treat (ITT) approach).

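### SAP 7.6 lets later treatment decide whether days 7–30 of an interruption, and events in them, count in the as-treated analyses, and leaves deaths in that window undefined

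*SAP*

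**What the plan says.** Protocol 9.7.2.1 makes the comparison as treated: "The primary comparative analyses will be based on the actual anticoagulation treatment the patients receive". It defines a permanent stop "if other relevant anticoagulation treatment is initiated or otherwise dependent on the duration of treatment interruption" and leaves the detail to the SEAP.

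The Objective 2 SAP supplies that detail in 7.6, under incidence rates. For patients who finish planned treatment early or stop for good, the text reads: "will be censored at date of last drug intake + 6 days for both DE and VKA". An earlier start of a different anticoagulant brings the censoring date forward to that day. A stop is permanent "if other relevant anticoagulation treatment is initiated or if treatment has been interrupted for more than 30 days". Item 2a of the same section repeats the rule for the multivariable Cox model: "censored at date of last drug intake + 6 days for both dabigatran etexilate and VKA or at first intake of another relevant anticoagulation treatment".

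Item 1, the overlap-weighted Cox model that is the main analysis, does not restate the rule. It applies there all the same. Protocol 9.7.2.1 makes the primary comparison as treated, and item 2b defines the ITT sensitivity run by contrast with the main model: "Cox regression analysis (based on the main analysis model) will be performed without censoring at permanent discontinuation".

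Neither document says how an event or a death inside an interruption is handled.

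**The concern.** The censoring date lies up to 24 days before the information that triggers it. On gap day 7 nobody can know whether the patient is still at risk; that is settled by a later resumption, a later switch, or the passing of day 30. Time at risk should depend only on what has happened up to that time.

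The dependence matters because an outcome can itself change what follows. A bleed or a recurrence in the gap may prompt a different drug, no drug, or a quick return to the same drug. The rule then keeps or deletes the event according to that choice, while event-free gap time is kept only for patients who resume. If resumption or switching habits differ between DE and VKA, the distortion does not cancel in the hazard ratio.

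Deaths add a separate gap. A patient who dies in the interruption without a switch has neither started another drug nor been interrupted for more than 30 days.

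**Working it through.** The rule has no stated figure to reproduce, so it is first applied as written to example patients.

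**Step 1. Example histories.** Last intake on day 100. If the stop is permanent, the censoring date is the earlier of day 106 and first intake of another anticoagulant.

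| Event | What follows | Permanent? | Censored | Event counted? |
|---|---|---|---|---|
| (a) day 115 | same drug resumed day 118 (gap 18 days) | no | not at the gap | yes |
| (b) day 115 | switch day 116 | yes | day 106 | no |
| (c) day 115 | nothing resumed | yes | day 106 | no |
| (d) day 110 | same drug resumed day 140 (gap 40 days) | yes | day 106 | no |
| (e) day 100 | switch day 101 | yes | day 101 | yes |
| (f) day 103 | switch day 104 | yes | day 104 | yes |
| (g) fatal, day 115 | no switch, gap 15 days | neither condition met | undefined | by the letter, yes |

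Rows (a) to (c) share one history up to the event and differ only afterwards. Rows (e) and (f) show that events on drug or within 6 days of last intake are kept even when they cause a switch.

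**Step 2. Direction.** The documents give no interruption data, so these inputs are assumptions: event hazard h = 0.15 per year after gap day 6; 70% of event-free gaps resumed, uniformly over days 7–30; after an event a share r resumes the same drug in time.

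- Actual window time per gap (resumers average 12 days, the others 24): 0.7 × 12 + 0.3 × 24 = 15.6 days.
- Window time the rule keeps: 0.7 × 12 = 8.4 days.
- Share of window events kept: r.
- Estimated window rate ≈ h × r × 15.6 / 8.4 = 1.857 × r × h.

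| r | Window events kept | Estimated rate per year (true 0.15) |
|---|---|---|
| 0.2 | 20% | 0.056 |
| 0.5 | 50% | 0.139 |
| 0.54 (= 8.4 / 15.6) | 54% | 0.15 |
| 0.6 | 60% | 0.167 |
| 0.7 | 70% | 0.195 |

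Simulation of this set-up agrees to within about 0.002. The sign changes at r ≈ 0.54, below the 70% assumed for event-free gaps, so even an event that makes resumption less likely can push the rate up.

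A second set of assumptions (planned resumption uniform over 1–60 days, hazard 0.0005 per day, a share s switched after an event and the rest resuming the next day) keeps 97%, 72%, 49%, 24% and 0% of window events for s = 0, 0.25, 0.5, 0.75 and 1. The estimated window rate is then 3.3, 2.5, 1.7, 0.85 and 0 times the true rate.

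**Step 3. Between arms.** With equal hazards and equal event-free resumption, the ratio of window rates is r(DE) / r(VKA). Values of 0.5 and 0.7 give 0.71; reversed, 1.40. The true ratio is 1. This concerns the window only, not the overall hazard ratio.

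**Step 4. Yardstick for size.** Protocol Table 9.5:2 uses the Freedman formula with 5.3% against 7.7%, 90% power and one-sided alpha 0.025. With HR = 5.3 / 7.7 = 0.688, events = (1.960 + 1.282)² × (1.688 / 0.312)² ≈ 309. With 15% exponential loss the mean one-year event probability is 0.060, so N ≈ 5146, within 3% of the stated 5000. For every 1% of bleeding events that falls in the window (an assumed share), about 3 of 309 events are open to the rule; at r = 0.2 to 0.5 it would drop 50–80% of these, about 1.5 to 2.5 events.

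**The case against.** **These events are off treatment anyway.** The as-treated rule allows a 6-day tail, so an event on gap day 15 is not an on-treatment event, and dropping it is no loss. This stands, and it shapes the fix: the fault is that some such events and their gap time are kept, selected by later behaviour.

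**The rule could be applied at the event date.** On day 115 the interruption has lasted 15 days, so a first-event analysis might simply count the event. The SAP does not say so. If it did, every window event would count (r = 1) while event-free non-resumers were still cut back to day 6, and under the Step 2 assumptions the rate would read 1.857 × 0.15 ≈ 0.28. That reading does not remove the problem.

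**ITT runs are planned, the rule is the same in both arms, and the analyses are exploratory** (SAP 7.6; Protocol 9.7.1). All true, and this limits the weight of the point. The ITT runs keep every gap event but also add all other off-treatment time. They answer a different question and do not correct the as-treated estimate.

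**Stronger readings that the documents do not support.** A reader might infer that on-treatment rates are biased downward. Step 2 shows that the direction depends on resumption after an event, which is unknown. A reader might also infer that a gap event counts only if the drug is resumed; row (g) is the exception. Finally, a reader might take "All recurrent VTE require objective verification by definitive diagnostic evaluation" (Protocol 9.3.3) to mean that a recurrence treated on suspicion is lost because imaging follows the switch. That sentence sets what must be verified, not the date given to the event, and neither document dates a recurrence at confirmation.

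**Conclusion.** The point holds for days 7–30 of an interruption. As written, SAP 7.6 makes time at risk and event counting in that window depend on later treatment, and it does not define the handling of a death there. Through Protocol 9.7.2.1 and SAP item 2b this reaches the main comparison of both primary outcomes.

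The as-treated rates and hazard ratio can be biased up or down, and unequally by arm if resumption or switching differs. The size cannot be computed from the documents. It is probably small, a few events on the design's own event count if the window holds about 1% of bleeding events, but that share is an assumption. The sample size is unaffected. This is a minor point, worth correcting because the correction is cheap.

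**What to change.** In SAP 7.6, for all as-treated rates, Kaplan-Meier curves and Cox models, including the overlap-weighted main model:

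- End time at risk at last intake + 6 days, or at first intake of another anticoagulant if earlier, for every interruption, whatever happens later.
- Count events and deaths only up to that date.
- Let patients who are still free of the outcome re-enter by delayed entry when the same drug is resumed, using counting-process (start, stop) data. A patient with a gap event does not re-enter for that outcome.
- State in item 1 that the rule applies to the main model.

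In Step 1, rows (a) to (d) and (g) then all end at day 106 with the gap event not counted, and rows (e) and (f) still count. Keep the ITT runs as they are, so gap events remain visible there.

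The cost is a few sentences, a restructured analysis data set, and a small loss of person-time and of gap events now counted. The treatment start and stop dates needed are already collected under Protocol 9.3.1.1 and 9.3.1.3. The change removes the dependence on the future; it does not make the decision to stop treatment unrelated to risk, which remains a limit of any as-treated analysis.

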#### **9.7.2.1 Main analyses**

For Objective 1:

Baseline patient demographics and disease characteristics, including information regarding the index VTE event, medical history, concomitant therapies, and laboratory data as specified in [Section 9.3.1](#), will be summarized descriptively for all eligible patients overall and by anticoagulation treatment at baseline. The analysis will be repeated by region and by additional relevant patient attributes.

Patterns of anticoagulation treatment at baseline will be described overall, by region, and by additional relevant patient attributes.

For Objective 2:

Patient demographics and disease characteristics at baseline as described above for Objective 1 will be summarized descriptively for all eligible patients by their initial anticoagulation treatment (i.e. dabigatran etexilate or VKA). This analysis will be repeated by region and by additional relevant patient attributes.

Given the observational nature of this study, patients in the dabigatran etexilate and VKA groups may differ with regard to important baseline demographics and disease characteristics. When the target sample size is reached, propensity scores that estimate the probabilities that patients would be initiated on dabigatran etexilate will be calculated using a logistic regression model that considers variables that are risk factors for the occurrence of VTE or bleeding events or affect the choice of anticoagulation treatment (details of the model will be provided in the SEAP). Overlap of propensity scores between the dabigatran etexilate and VKA groups will be examined to assess the comparability of the two patient populations, and to estimate the loss of patients from the comparative analysis if trimming or matching is to be performed.

The primary safety and effectiveness outcomes will be analyzed for dabigatran etexilate patients in comparison to VKA patients using Cox proportional hazards models. Confounding will be controlled for using appropriate methods, including adjustment of covariates in the Cox regression model, trimming of extreme observations, and/or propensity score matching, based on the evaluation of the comparability of dabigatran etexilate and VKA patients (i.e. overlap of propensity scores) as described above. Details of the analytical methods and the selection rules of the appropriate analysis strategy will be provided in the SEAP.

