7. PLANNED ANALYSIS

The propensity scores will be estimated after the multiple imputation is performed based on eligible patients who took the prescribed treatment at least once. A logistic regression model will be used to model the probability of receiving dabigatran etexilate in comparison to vitamin K antagonist, i.e. high propensity scores, close to 1, indicate a higher probability of dabigatran use. See Section 7.6 for details.

For the main analysis, only those patients will be included who have a shared range of ePS. This patient set is denoted as the **restricted patient set in the SEAP**. Patients with ePS outside the overlapped ePS range will be trimmed (or excluded).

Safety analyses will be conducted for the all eligible treated patient set.

Summary statistics for continuous variables will include the number of observations (N), mean, standard deviation (SD), minimum, Q1 (25th percentile), median, Q3 (75th percentile), and maximum; tabulations of categorical variables will present all possible categories and will display the number of observations per category as well as percentages. The default precision for percentages should be one decimal place, unless otherwise specified. In general, percentages will be based on the number of patients eligible for the particular analysis, whether they have missing data or not. A category 'Missing' will be displayed whenever at least one patient falls within this category.

Data collected in the baseline eCRFs (informed consent, patient status, demographics, inclusion/exclusion criteria, vital signs and physical assessment, clinical signs and symptoms) will be considered as respective baseline values. Data collected in the hospital discharge related eCRFs will be summarized for the hospital discharge time point. Despite the fact that the analysis is of cross-sectional nature, data collected in eCRFs at hospital discharge will also be summarized in the descriptive analysis.

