For the further outcome events such as Recurrent DVT and/or PE, VTE-related mortality, All-cause mortality, Life-threatening bleeding events, Acute coronary syndrome, and Net clinical benefit, incidence rates, KM estimates and KM curves will be calculated for the eligible patients who took the prescribed treatment at least once for both treatment groups. Additionally, above analyses will be performed on the restricted patient set.

Technical specifications

Incidence rates per 100 patient years with 95%-confidence intervals for important outcome events (single and composite outcome) will be calculated the following way. In addition, these analyses will be done stratified by ongoing chronic antiplatelet treatment at baseline. Recurrent events will be disregarded for calculation of incidence rates. Incidence rate λ is defined as

$$\begin{aligned} \text{Incidence rate } \lambda \left[\frac{1}{100} \text{ pt. yrs} \right]: \\ = 100 * \frac{\text{number of patients with event}}{\frac{1}{365.25} * \sum_{\text{patients}} \text{person time at risk(event)}[\text{days}]} \end{aligned}$$

where the denominator is the patient years under risk. The 2-sided 95% CI of λ will be calculated based on the Poisson distribution and its relationship with the Chi-square distribution according to the following formula [7]

$$[\lambda_{\text{lower}}, \lambda_{\text{upper}}] = [\{0.5 \chi^2(\alpha/2; 2x)\}/n, \{0.5 \chi^2(1 - \alpha/2; 2x + 2)\}/n],$$

where $\chi^2(\gamma, r)$ is the 100 γ th the percentile of a chi-square distribution with r degrees of freedom, n is the patient years under risk for the event, x is the number of patients with event, and α for $(1 - \alpha)\%$ 2-sided CIs.

Cumulative risk is defined as cumulative proportion of patients with event and will be calculated as the Kaplan-Meier estimate for failure. The Kaplan-Meier curve will be plotted. The proportion of patients with event, as well as the proportion of censored patients falling into specified intervals and the Kaplan-Meier estimate for failure will be computed for the following categories:

- ≤ 3 months
- $3 <$ and ≤ 6 months
- $6 <$ and ≤ 12 months
- > 12 months

Distribution and overlap of the ePS between the two groups

The ePS is the probability of a patient being in one of the two treatment groups, conditional on relevant observed baseline variables. For this analysis, the ePS for being in the DE group vs. VKA group will be estimated using the multivariable logistic regression model.

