In the following if not stated otherwise for all analyses only patients from the restricted patient set are considered.

- 1.) Main analysis of the main outcomes (Major bleeding and clinically relevant non major bleeding, and symptomatic recurrent VTE including VTE-related mortality)

The main analysis will be a PS analysis using overlap weights. A Cox regression model including the overlap weights will be performed. In addition, the main outcomes will be analyzed within the subgroups defined in Section 6.4, when the number of patients per treatment group is at least 500. For the overlap weights analysis each patient in the treatment groups DE and VKA will be weighted proportional to the probability of that

patient being assigned to the opposite treatment group. The weights are called “overlap weights” and are calculated as follows:

$$\begin{aligned} O_{DE} &= 1 - P \\ O_{VKA} &= P \end{aligned}$$

where P is the estimated propensity score of a patient being assigned to the DE treatment group.

To assess baseline imbalance for the overlap weights by ePS, the mean of each covariate of interest will be calculated for patients in each of the treatment groups (DE and VKA). For binary variables, the proportion will be used instead. For categorical variables with more than two categories, dummy binary variables will be derived to represent each category and the proportion calculated for each of the treatments.

The standardized differences will be calculated for the mean for each covariate and the standardized differences (denoted as d) for the mean of a continuous variable is defined [10] as:

$$d = \frac{(\bar{x}_{DE} - \bar{x}_{VKA})}{\sqrt{\frac{s^2_{DE} + s^2_{VKA}}{2}}}$$

where \bar{x}_{DE} and \bar{x}_{VKA} denote the sample mean of the covariate in DE and VKA patients, respectively, while s^2_{DE} and s^2_{VKA} denote the sample variance of the covariate in DE and VKA patients, respectively.

For dichotomous variables, the standardized difference is defined as:

$$d = \frac{(\hat{p}_{DE} - \hat{p}_{VKA})}{\sqrt{\frac{\hat{p}_{DE} * (1 - \hat{p}_{DE}) + \hat{p}_{VKA} * (1 - \hat{p}_{VKA})}{2}}}$$

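### The Kaplan-Meier curves, cumulative risks and incidence rates that compare dabigatran with VKA on the restricted set carry no overlap weights, so they are not adjusted for measured imbalance and may disagree with the weighted hazard ratio

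*SAP*

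**What the plan says.** Section 7.6 of the Objective 2 SAP asks for incidence rates and cumulative risks by treatment for the main and secondary outcomes, with curves plotted "for a graphical comparison Kaplan Meier curves". The population is given next: "These statistics will be calculated on the restricted patient set, and patients who never took the prescribed treatment will not be included". Sections 6.3 and 7 define the restricted set as treated eligible patients whose estimated propensity score (ePS) lies in the range shared by both groups; patients outside it are dropped.

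The technical specifications in 7.6 then fix the calculations. The rate is patients with an event over person-time, with an exact chi-square (Poisson) interval in which "x is the number of patients with event". For risk: "Cumulative risk is defined as cumulative proportion of patients with event and will be calculated as the Kaplan-Meier estimate for failure".

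Weights come later in the same section: "The main analysis will be a PS analysis using overlap weights", followed by "A Cox regression model including the overlap weights will be performed". A dabigatran patient gets weight 1 − P and a VKA patient gets P, where P is the ePS for dabigatran. Beyond the Cox model, the only other use given for the weights is the covariate balance check.

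Protocol 9.7.2.1 warns that "patients in the dabigatran etexilate and VKA groups may differ with regard to important baseline demographics and disease characteristics", and Protocol 9.9 names channelling bias.

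**The concern.** The study's second question is comparative, and readers take absolute risk from the curves and the cumulative risks. In this plan the hazard ratio is adjusted for about thirty measured covariates, while the curves beside it are adjusted for none. Trimming may look like adjustment but is not: it removes patients with no counterpart in the other group and leaves the mix of the remaining patients almost as it was.

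The report could therefore show separated curves next to a hazard ratio near 1, or an absolute difference that is too large or too small for the hazard ratio printed with it. If higher-risk patients were channelled to dabigatran, the curves could suggest harm that the adjusted analysis does not show. If they were channelled to VKA, the curves could hide harm.

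**Working it through.** **1. Does any formula carry a weight?** Setting the parts of SAP 7.6 side by side:

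| Output on the restricted set | Calculation given | Weight |
|---|---|---|
| Incidence rate | 100 × patients with event ÷ patient-years | none |
| Interval for the rate | exact, from chi-square quantiles on the count x | none |
| Cumulative risk and curve | ordinary Kaplan-Meier | none |
| Repeat without censoring at discontinuation (ITT) | same rates and curves | none |
| Cox model, main analysis | overlap weights 1 − P and P | yes |

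The SAP does not use the word unweighted; that follows from the formulas. An exact Poisson interval needs an integer count, so it could not be meant for weighted data.

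**2. Scale.** This point disputes no stated figure. Protocol 9.5 supplies the scale: 5000 patients, 1:1, VKA risk 7.7%, hazard ratio 0.69, 15% loss, 90% power, one-sided 0.025.
- Freedman events: (1.960 + 1.282)² × (1.69/0.31)² = 312.3, so 313.
- Hazards: VKA −ln(1 − 0.077) = 0.0801; dabigatran 0.69 × 0.0801 = 0.0553; loss, spread over the year, −ln(0.85) = 0.1625.
- At N = 5000 about 302 events are expected. Power = Φ(√302 × 0.31/1.69 − 1.960) = 89.0%, which agrees with the stated 90% to within rounding of the hazard ratio.

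**3. Closed form, one binary confounder.** If the confounder multiplies the rate by R, the unweighted ratio equals the true ratio times

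[1 + p_DE(R − 1)] ÷ [1 + p_VKA(R − 1)].

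Both levels of the confounder occur in both groups, so trimming on the score removes nobody. Assume p_VKA = 20% and R = 2 to 3:

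| Standardized difference | p_DE | Factor | True 0.69 appears as | Factor if the prevalences are swapped |
|---|---|---|---|---|
| 0.10 | 16.2% | 0.97 to 0.95 | 0.67 to 0.65 | 1.03 to 1.06 |
| 0.25 | 11.0% | 0.93 to 0.87 | 0.64 to 0.60 | 1.08 to 1.15 |
| 0.50 | 4.2% | 0.87 to 0.77 | 0.60 to 0.53 | 1.15 to 1.29 |

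For example, at 0.25 with R = 2: 1.110 ÷ 1.200 = 0.925, and 0.69 × 0.925 = 0.64.

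**4. Simulation with the SAP's steps.** There were 150 runs per setting with N = 5000, a logistic ePS, trimming to the common range, and then unweighted against overlap-weighted results. The assumptions are four binary confounders and one continuous one, each with a rate ratio of 1.5 or 2, all more frequent or higher in the VKA group. Trimming removed 0.1% to 0.3% of patients. The largest standardized difference in the trimmed set is in the first column; after overlap weighting it was about 0.004.

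| Largest std. difference | Unweighted rate ratio, true 1.00 | Unweighted rate ratio, true 0.69 | One-year risk difference in points (VKA minus dabigatran), true 0.69: unweighted / weighted |
|---|---|---|---|
| about 0.10 | 0.89–0.94 | 0.64–0.65 | 2.6 / 1.9–2.2 |
| about 0.24 | 0.77–0.86 | 0.52–0.59 | 3.1–3.4 / 1.9–2.1 |
| about 0.46 | 0.60–0.75 | 0.42–0.52 | 3.6–4.1 / 1.6–1.9 |

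The weighted rate ratio was 1.00–1.03 when the truth was 1.00 and 0.69–0.72 when it was 0.69, and it agreed with the weighted Cox hazard ratio. With no true effect, a largest difference of 0.24 and rate ratios of 2, the unweighted curves were 1.6 points apart at one year and the weighted ones −0.1.

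The simulated bias exceeds the closed form because five confounders act in the same direction.

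**The case against.** The best defence is that the plan separates description from comparison. Protocol 9.7.1 says follow-up data are summarised descriptively, assigns the comparison to regression and propensity-score methods, and calls all analyses exploratory. The overlap-weighted Cox model is named as the main analysis. No test, rate ratio or risk difference is attached to the curves. Crude results beside an adjusted hazard ratio are ordinary reporting, and disagreement between them is not in itself an error. This limits the seriousness of the point. It does not remove it, because the SAP itself gives the curves a comparative purpose and does not mark them as crude.

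A reader might go further in four ways, none of which the documents support:
- **That these are the only absolute risks or the only comparative figure.** Sections 5.3, 6.4 and 7.7 are not visible, so a weighted version there cannot be excluded. SAP 7.6 also plans a subgroup display on the eligible set, and says the overlap-weights analysis might be run for all outcomes.
- **That the curves carry the whole channelling bias.** Protocol 9.1 asks for balanced enrolment by treatment and index event, ideally at the same site and at similar times. The extent of the remaining imbalance is unknown.
- **That the weighted hazard ratio is free of bias.** Weighting deals with measured covariates only, and Protocol 9.9 accepts that unmeasured confounding may remain.
- **That the curves will favour dabigatran.** The channelling example in Protocol 9.9 sends high-risk patients to dabigatran, which would push the bias the other way.

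**Conclusion.** The point holds for the displays and not for the main analysis. In the visible text, the restricted-set rates, cumulative risks and curves meant for comparing the two groups are unadjusted for measured imbalance that the protocol expects, and they may not match the weighted hazard ratio, which is itself unaffected.

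The absence of weights can be read directly from the formulas. The size cannot: the documents give no imbalance figures. Under the assumptions in step 4, with largest standardized differences of about 0.10 to 0.24, a true ratio of 1 would appear as about 0.77 to 0.94. The 0.46 row shows a more extreme case. With channelling towards dabigatran the ratios would lie above 1. This should be changed, but no decision rule or confirmatory claim depends on it.

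**What to change.** In SAP 7.6, for the restricted set, add:
- Kaplan-Meier curves, cumulative risks and incidence rates computed with the Cox model's overlap weights (1 − P for dabigatran, P for VKA). The weights apply to events, to the numbers at risk and to person-time: rate = 100 × Σ(weight × event) ÷ Σ(weight × patient-years).
- Robust or bootstrap confidence intervals for these, because the exact Poisson interval does not apply to weighted counts.
- A statement that the weighted curves serve the graphical comparison, and that the present outputs are kept and labelled crude or descriptive.

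Weighted risk differences at 3, 6 and 12 months would match the intervals already in 7.6, but they are optional because the visible plan does not ask for a risk difference.

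The cost is SAP wording and modest programming; the weights already exist and no new data are needed. One consequence should be stated in the report: the weighted risks describe the overlap population, not all treated patients, which is a further reason to keep the crude figures.
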